Adverse events will be mapped to preferred terms and body systems using the Medical Dictionary for Regulatory Activities (MedDRA) coding dictionary. While the primary presentation of adverse events will be subject-based, the number of adverse events will also be reported. The number and percentage of subjects reporting each event will be summarized during the treatment period by treatment assignment. Incidence of adverse events by maximum reported severity will also be tabulated. Serious adverse events and adverse events leading to discontinuation will be displayed.

D. Eligibility Criteria

Eligibility for participation in this study will be based on the inclusion/exclusion criteria. An individual subject may only be included in the study once.

1. Inclusion Criteria

- 1. Subject age is greater than or equal to 22 years and less than 80 years of age.
- 2. Subject has documented Type 1 or Type 2 diabetes mellitus (receiving insulin, diet controlled, or taking parenteral hypoglycemic agents)
- 3. Subject is on a stable antidiabetic regimen (medication and/or diet) to control their diabetes for at least 30 days prior to Screening.
- 4. Subject has an HbA1c <10% at Screening or within 2 months of Screening.
- 5. Subject has daily pain attributed to bilateral symmetrical Diabetic Peripheral Neuropathy with numbness, tingling, and/or burning based on clinical judgement for at least 6 months prior to screening.
- 6. Subject's pain or discomfort from DPN is identifiable.

- 7. Subject is in pain Phase 2, 3, or 4 as per the Phasing of Neuropathy Scale.
- Subjects average pain over the last 24 hours is ≥3 based on the 11-point Numeric Pain Rating Scale (NPRS) at the Screening Visit.
- 9. Subject has adequate lower extremity pulse in both feet and no intermittent claudication.
- 10. Subject is able to ambulate independently with assistive devices, but not wheel chair bound.
- 11. Subject is willing and able to give written informed consent and to comply with all parts of the study protocol.
- 12. Female subjects must be post-menopausal, surgically sterile, abstinent, or practicing (or agrees to practice) an effective method of birth control if they are sexually active for the duration of the study (Effective methods of birth control include prescription hormonal contraceptives, intrauterine devices, double-barrier methods, and/or male partner sterilization).

2. Exclusion Criteria

- 1. Subject is in pain Phase 1 or 5 as per the Phasing of Neuropathy Scale.

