- 18. Subject has an implanted pacemaker, defibrillator, neurostimulator, spinal cord stimulator, bone stimulator, cochlear implant, or other implanted device with an implanted metal lead(s).
- 19. Subject is currently pregnant or planning on becoming pregnant prior to Day 121.
- 20. Subject has previously treated with PROVANT[®] Therapy System within 60 days on the lower extremity.
- 21. Subject is unwilling or unable to follow study instructions or comply with the treatment regimen, diary documentation, and study visits.
- 22. Subject has pain from any other source that can confuse the assessment of the pain associated with DPN.
- 23. Subject has a clinically significant foot deformity (Charcot's syndrome or club foot).

- 24. Subject has received nerve blocks for neuropathic pain within 4 weeks of the Screening Visit.
- 25. Subject has been diagnosed with mononeuropathy.
- 26. Subject has a skin condition that could alter their sensation.
- 27. Subject has had a previous surgery to the spine or lower extremity with residual symptoms of pain or difficulty with movement.
- 28. Subject has moderate or severe arthropathy (RA, OA, Gout) that causes discomfort during casual walking or stair climbing.

E. Recruitment

Recruitment for study subjects will be drawn from the patient population at the investigative study site. Recruitment efforts will be supplemented with IRB approved internet, radio and/or print advertising as necessary.

F. Randomization

The schedule for randomization of subjects and allocation to treatment will be prepared using SAS[®] (Statistical Analysis System; Cary, NC) to create a computer-generated scheme based on a permuted block algorithm. The randomization schedule will randomize in a 1:1 ratio (active : sham) to a device based on the randomization kit numbers. The kit numbers will be assigned sequentially to subjects that qualify for inclusion into the study.

G. Device Description

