pressure in the angiosome is made. SPP (mmHg) at reactive hyperemia is recorded. A second measure of SPP will be obtained on the plantar aspect of the right foot directly below the location where the SPP was performed on the dorsal aspect of the right foot. SPP will be conducted at the Enrollment Visit, Day 61, and end of study visit (Day 121). An increase in SPP would be considered clinically meaningful.

Pain Intensity (PI): a validated 11-point Numeric Pain Rating Scale (NPRS) with scores (0-10) collected as patient-reported outcomes on a paper diary, at Screening for eligibility, at the Enrollment Visit for a baseline value, and Days 61, 75 and 91 to assess response (1-point decrease from baseline in average pain score over the last 24 hours). On the diary, PI will be assessed after each morning ($8am \pm 2$ hours) treatment. Subjects will report their average pain score over the last 24 hours. Diaries will be distributed and collected from the subjects every 2 weeks to ensure compliance.

Brief Pain Inventory (BPI): is a 32-question long form questionnaire that assesses the severity of pain and its impact on specific daily functions. Cronbach's alpha reliability ranges from 0.77-0.91. The BPI long form will be administered at the Enrollment Visit, Day 30, 61, 91, and end of study visit (Day 121). The change from baseline will be captured and assessed.

Brief Fatigue Inventory (BFI): is a 4-question assessment that assesses the level of fatigue and the impact of the fatigue on daily function over the last 24 hours. A global fatigue score is collected by averaging all items on the BFI. Cronbach's alpha reliability ranges from 0.82-0.97. BFI is patient reported and collected at the Enrollment Visit, Days 30, 61, 91, and end of study visit (Day 121). The change from baseline will be captured and assessed.

Patient Global Impression of Change (PGIC): a 7-point validated categorical scale of overall change in status since initiation of treatment with the study device. PGIC allows subjects to integrate into one overall evaluation of the different aspects of their response to treatment, including pain reduction, improvement in functioning and side effects. PGIC will be collected every 7 days in the paper diary, immediately following the morning treatment. PGIC serves to anchor within-subject changes in pain over the course of treatment.

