- 1. Conduct VPT
- 2. Conduct QST
- 3. Collect diary and dispense a new diary for the next two weeks
- 4. Review and record adverse events
- 5. Review and record all concomitant medications
- 6. Assess adherence to PEMF treatment regimen by monitoring the usage meter
- 7. Assess treatment satisfaction

G. Day 61 Visit (Day 61 +3 Days)

Subjects will return to the clinic on Day 61 with their devices. At this visit, the following procedures will be performed:

- 1. Conduct VPT
- 2. Conduct QST
- 3. Measure blood glucose
- 4. Conduct SPP
- 5. Collect BPI, BFI, HADS
- 6. Collect subject's average pain score
- 7. Collect diary and dispense a new diary for the next two weeks
- 8. Review and record adverse events
- 9. Review and record all concomitant medications
- 10. Assess adherence to PEMF treatment regimen by monitoring the usage meter
- 11. Assess treatment satisfaction
- 12. Assess response
 - If a subject is determined to be a responder (based upon a 1-point decrease in average pain score over the last 24 hours using the NPRS) return the active devices and randomize the subject per the schedule.
 - If the subject is determined to be a non-responder, instruct the subject to continue treating with the active devices and dispense additional DACs.

H. Day 75 Interim Visit (Day 75 + 3 Days)

Subjects will return to the clinic on Day 75 with their devices. At this visit, the following procedures will be performed:

- 1. Conduct VPT
- 2. Conduct QST
- 3. Collect subject's average pain score (if non-responder at Day 61)
- 4. Collect diary and dispense a new diary for the next two weeks
- 5. Review and record adverse events
- 6. Review and record all concomitant medications
- 7. Assess adherence to PEMF treatment regimen by monitoring the usage meter
- 8. Assess treatment satisfaction
- 9. Assess response for non-responders at Day 61
 - If a subject is determined to be a responder (based upon a 1-point decrease in average pain score over the last 24 hours using the NPRS) return the active devices and randomize the subject per the schedule.
 - If the subject is determined to be a non-responder, instruct the subject to continue treating with the active devices and dispense additional DACs.

I. Day 91 Visit (Day 91 +3 Days)

Subjects will return to the clinic on Day 91 with their devices. At this visit, the following procedures will be performed:

- 1. Conduct VPT
- 2. Conduct QST
- 3. Measure blood glucose
- 4. Collect BPI, BFI, HADS

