Randomization of subjects can occur at different times, depending on when the subject is determined to be a responder. Once a subject is determined to be a responder (based upon a 1-point decrease in average pain score over the last 24 hours using the NPRS), the subject will return the active devices and be randomized 1:1 to receive active treatment or inactive sham devices and be instructed to treat through study day 120. If a subject is determined to not be a responder at Day 91, i.e., their final chance to be randomized, the subject will be terminated from the study at the end of the Day 91 visit.

C. Summarization of Results

The tabulations will be based on the paired results for the change from the baseline to study day 120 for patients who are randomized, and separately for the last observation. Supportive subject data listings will be sorted and presented by subject number, visit date and relative study day. Listings will also include the number of days relative to the initiation of treatment. Two sets of analyses will be generated; summary tabulations for all randomized subjects who complete the baseline and study day 120 evaluations (*Completers Analysis Set*), and all randomized subjects using the baseline and last recorded set of evaluations (*End of Study Evaluation Set*). This latter set should include all subjects who were randomized and complete at least one set of evaluations after randomization.

Specific algorithms will be described in the Statistical Analysis Plan for imputing missing or partially missing dates, if deemed appropriate, under specific data topics. Imputed or derived data will be flagged in the individual subject data listings. Imputed data will not be incorporated into any raw or primary datasets. The imputed data will be retained in the derived / analysis datasets.

The total duration for a subject *on-study* will be calculated as the difference between the date of initial study treatment in the *Induction Phase* and the last day of observation plus 1 day. All calculations for defining the duration on-study will follow the algorithm DURATION = [STUDY COMPLETION OR WITHDRAW DATE – INITIAL TREATMENT DATE + 1].

Summary statistics will consist of the count and percentage in each level for categorical variables, and the sample size (n) mean, median, standard deviation (SD), minimum, and maximum values for continuous variables. All mean and median values will be formatted to one more decimal place

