- Increased bleeding at surgical site
- Chilliness
- Headache
- Malaise
- Nausea
- Abdominal or chest wall discomfort
- Muscle cramps
- Excessive menstruation
- Failure to reduce pain or an increase in pain

² Reported at least once since market launch in 2004.

C. Unanticipated Adverse Device Effect (UADE)

Unanticipated Adverse Device Effect means any serious adverse effect on health or safety or any life-threatening problem or death caused by, or associated with, a device, if that effect, problem, or death was not previously identified in nature, severity, or degree of incidence in the protocol or informed consent form, or any other unanticipated serious problem associated with the device that relates to the rights, safety, or welfare of subjects. The protocol will contain all of the anticipated Adverse Events that could be associated with the study.

All UADEs must be reported *immediately* (within 24 hours of knowledge of the event) by telephone and fax to the following:

Sponsor Medical Contact – [name], MD; Regenesis Biomedical Inc.; [contact]; [contact]; [contact]

The investigator will follow up with a written description of the UADE submitted to the sponsor within 3 days, including the results of the UADE investigation and any treatment(s) provided.

Any UADE occurring up to the date of the final Follow-up Visit will be followed until it resolves, the investigator assesses the subject's status to have returned to baseline, or until the investigator feels that the event is stable and chronic.

The investigator shall submit to the reviewing IRB a report of any UADE occurring during an investigation as soon as possible in accordance with the IRB submission guidelines, but in no event later than 10 working days after the investigator first learns of the effect.

XI. INVESTIGATOR'S FILES/RETENTION OF DOCUMENTS

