APPENDIX C – SUBJECT DIARY FOR DAILY PAIN SCORE AND WEEKLY GLOBAL IMPRESSION OF CHANGE

PATIENT: _____ Week Start Date: _____

Treat Both Feet, Simultaneously, Twice Daily for 30 minutes, 8am +/- 2 hours and 8pm +/- 2hours.

Circle the Pain Score which represents your average Pain over the last 24 hours after completing your Morning (am) treatment.

On the scale below, a score of 0 represents No Pain whereas a score of 10 represents the Worst Possible Pain. Every 7 days, mark your overall status compared to the start of the study.

			0	l 2 Mild	3	4 5 Mode	6 rate	7 8	3 9 Severe	10		
		No Pain										Worst Possible Pain
Date:		0	1	2	3	4	5	6	7	8	9	10
Date:		0	1	2	3	4	5	6	7	8	9	10
Date:		0	1	2	3	4	5	6	7	8	9	10
Date:		0	1	2	3	4	5	6	7	8	9	10
Date:		0	1	2	3	4	5	6	7	8	9	10
Date:		0	1	2	3	4	5	6	7	8	9	10
Date:		0	1	2	3	4	5	6	7	8	9	10
	Since the start (check one bo	t of the	study,	my ove	rall sta	tus is:						
	Very Muc	h Wors	e	Muc	h Wor	se [Mini	mally V	Vorse	  1	lo Chai	nge
	🗌 Mi	nimall	y Impro	oved	🗌 Mu	ich Imp	roved		Very M	uch Imp	proved	

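### The NPRS wording names no body site or cause, so unrelated pain can occasionally change responder status at the 1-point gate and adds noise to the secondary pain endpoint

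*Combined protocol and SAP*

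**What the plan says.** The NPRS has three uses, and its descriptions are equally general in each.

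- **Entry.** Inclusion 8 reads "Subjects average pain over the last 24 hours is ≥3 based on the 11-point Numeric Pain Rating Scale (NPRS) at the Screening Visit".
- **Gate to randomisation.** Section III.L.2 defines response as a "1-point decrease from baseline in average pain score over the last 24 hours". Section VI.B repeats the rule: "based upon a 1-point decrease in average pain score over the last 24 hours using the NPRS". The score is taken in clinic at Enrollment and at Days 61, 75 and 91. The visit lists say only "Collect subject's average pain score" and do not reproduce the item put to the subject.
- **Secondary endpoint.** Under Pain Intensity, "Subjects will report their average pain score over the last 24 hours" in a daily paper diary. Appendix C gives the only subject-facing item text: "Circle the Pain Score which represents your average Pain over the last 24 hours after completing your Morning (am) treatment".

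Elsewhere the protocol is specific about the pain it means. Inclusions 5 and 6 require daily pain attributed to bilateral DPN that can be identified as such. Exclusion 22 applies when "Subject has pain from any other source that can confuse the assessment of the pain associated with DPN". Section IV.N has the reason for each analgesic recorded, separating neuropathic pain from, for example, headache. No matching step exists for the pain score.

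**The concern.** The instrument is broader than its target. A subject with a headache or back strain on the assessment day can properly answer the item as written by including that pain. Exclusion 22 works at Screening and Enrollment, while ratings run to Day 120.

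Two things are exposed. The first is the gate: one 24-hour rating, compared with one baseline rating, with a 1-point threshold. New pain on a visit day can mask a real fall in foot pain. The subject then waits for the next look, so the randomised period shrinks from 60 days to as little as 30, or the subject is terminated if masked again at Day 91. Unrelated pain on the baseline day would do the reverse and favour a false response at every look.

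The second is the pain endpoint. Neither the Day 121 procedures (Section IV.K) nor Appendix A schedules a clinic NPRS at Day 121. The end-of-treatment value can come only from the diary, so the diary wording matters even though the diary is not the gate.

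**Working it through.** **1. Wording, side by side**

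| Place | Site or cause named? |
|---|---|
| Inclusion 8 | No |
| Pain Intensity definition (synopsis; III.L.2) | No |
| Response rule (synopsis; III.K; IV.G to IV.I; VI.B) | No |
| Appendix C diary item | No |
| Clinic NPRS item | Text not given; described without site or cause |
| Inclusions 5 and 6; Exclusion 22; analgesic record (IV.N) | Yes, DPN |

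**2. The plan's own figure.** There is none to reproduce. Section VI.E gives 40 subjects as a convenience sample, without power or variance inputs. Everything below is illustration on stated assumptions.

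**3. Gate misclassification, by simulation.** Assumptions: baseline foot pain 3 to 8; true change with mean −1 and SD 1.5 between subjects; visit noise SD 1; unrelated pain of severity 2 to 7 on an assessment day, baseline included, with probability q. The reported score is either the maximum or the mean of foot and other pain. A subject is misclassified when status on the reported score differs from status on foot pain alone. Results are scaled to 40 subjects reaching the gate.

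| q | Rule | One look: changed of 40 | Three looks: changed of 40 | Three looks: missed / false |
|---|---|---|---|---|
| 5% | max | 0.7 | 0.2 | 0.4% / 0.2% |
| 5% | mean | 1.0 | 0.9 | 1.1% / 1.2% |
| 10% | max | 1.3 | 0.5 | 0.8% / 0.5% |
| 10% | mean | 1.9 | 1.7 | 2.1% / 2.2% |
| 20% | max | 2.5 | 1.0 | 1.5% / 0.9% |
| 20% | mean | 3.7 | 3.2 | 4.0% / 4.1% |

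At one look, missed responses exceed false ones in every row (for example 4.9% against 1.4% at q = 20%, max rule). Over three looks the mean rule evens them out. That is partly because it lets a milder second pain pull the rating down, and partly because the model allows unrelated pain at baseline freely, which Exclusion 22 would largely prevent.

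**4. One subject whose foot pain truly fell 2 points.** Let σ be the within-subject SD of a rating, and let unrelated pain add 2 points on an affected visit.

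- Unaffected visit: Φ(1/(σ√2)) = 0.76, 0.68, 0.64 for σ = 1, 1.5, 2.
- Affected visit: Φ(−1/(σ√2)) = 0.24, 0.32, 0.36.
- One look at σ = 1.5, q = 10%: 0.9 × 0.681 + 0.1 × 0.319 = 0.645, against 0.681.
- Up to three looks sharing a baseline error b ~ N(0, σ²): 1 − E[(1 − p(b))³], with p(b) = (1 − q)Φ((1 + b)/σ) + qΦ((b − 1)/σ). At σ = 1.5, q = 10% this falls from about 0.89 to 0.87. Over σ = 1 to 2 and q = 5% to 20% the loss is about 0.7 to 3.4 percentage points.

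**5. Noise in the pain endpoint.** Added variance per rating is q(1 − q) × 2² = 0.19 to 0.64 for q = 5% to 20%. Against σ² of 1 to 4 that is a rise of about 5% (0.19/4) to 64% (0.64/1), and 16% (0.36/2.25) in the middle case. The standard error of the active-sham difference widens by at most the square root of the variance ratio: √1.05 = 1.02 to √1.64 = 1.28, and √1.16 = 1.08 in the middle case. The true effect is smaller, because between-subject spread in real change is untouched.

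**The case against.** The case against giving this much weight is a good one, and most of it stands.

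- A reader might infer that the item asks for pain of any kind. It does not; it is silent. It sits below an instruction to treat both feet, on a form used by people selected for daily, identifiable DPN pain, after site instruction whose content is not given. Many will answer about their feet.
- A reader might take the diary item as the gate. The gate is the clinic score, whose item text is not reproduced.
- A reader might infer that the protocol forecasts unrelated pain in these subjects, because Section X.B lists headache, abdominal or chest wall discomfort and "Muscle cramps". That list is footnoted as events reported at least once since 2004 and includes surgical-site bleeding. It is a catalogue across uses and gives no rate.
- The false-responder route needs confusing pain at baseline. Exclusion 22 bars that, and eligibility is checked again at Enrollment or on the same day if the visits are combined.
- A fall to 0.24–0.36 looks dramatic, but it applies only on an affected day at one look.
- A reader might infer bias in the active-sham contrast. Under blinding the noise should be similar in both arms, and the documents give no rates by arm that would suggest otherwise.
- VPT and QST are the primary endpoints, and no formal testing is planned.

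Adverse events and analgesic reasons are recorded, so some affected scores could be recognised. However, the statistical section and the response rule make no use of those records. What the objection does not remove is the mismatch itself: DPN pain is the stated target, the only subject-facing item does not ask for it, and entry criteria cannot screen out pain that starts later.

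**Conclusion.** The point holds as a modest measurement weakness with a cheap remedy. No NPRS description names a site or cause. Unrelated pain can occasionally change responder status, mainly by hiding or delaying a true response, and it costs some precision in one secondary endpoint.

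The size rests entirely on assumed frequency and severity of unrelated pain: about 0.2 to 3.2 of 40 subjects over three looks. The stronger reading, that such pain decides who is randomised, is not supported. Even at the top of that range, more than nine in ten subjects keep the status their foot pain alone would give (36.8 of 40). The primary endpoint measurements are not affected by the wording.

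**What to change.** Word the diary item in Appendix C and the clinic NPRS at Screening, Enrollment and Days 61, 75 and 91 as *average pain in your feet from diabetic neuropathy over the last 24 hours*. Put the same words in Inclusion 8 and in the response definition wherever it appears. Diary and clinic items must change together, because the pain endpoint sets a clinic baseline against a diary end value.

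If enrolment has begun, apply the new wording to newly enrolled subjects only. Keep the old wording for anyone whose baseline was taken under it; otherwise a change of question could itself produce or cancel a 1-point change. Record the wording version for each subject.

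The cost is a diary and CRF reprint, an IRB notification and, if enrolment has begun, two wording versions in the data. No visit, device or treatment schedule changes.

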APPENDIX D – INSTRUCTIONS FOR OBTAINING ANKLE-BRACHIAL INDEX

Measurement of Ankle-Brachial Index

- 1. Place the patient in the supine position, with the arms and legs at the same level as the heart, for a minimum of 10 minutes before measurement.
- 2. Select an appropriately sized blood pressure cuff for both the ankle and the arms (see the images below); the cuff width should be, at a minimum, 20% greater than the diameter of the extremity.
 - a. For the brachial systolic pressure, make sure you have appropriately sized upper-extremity cuff.
 - b. For the ankle systolic pressures, make sure that cuff completely encircles lower extremity. The ankle cuff should go on the leg between the malleolus and the calf. Enough room should be left below both cuffs to permit placement of the ultrasound gel, so that the Doppler device can adequately detect the brachial, dorsalis pedis (DP), and posterior tibial pulses (PT).
- 3. Obtain the brachial systolic pressures of both arms (see the images below), and choose the higher of the 2 values as the brachial systolic pressure (the difference between them should be less than 10 mm Hg). The brachial pulse is best appreciated on the medial side of the antecubital fossa.
- 4. Obtain the anterior tibial and posterior tibial systolic pressures of the extremity in question (see the images below), and select the higher of the 2 values as the ankle pressure measurement. The posterior tibial pulse is best appreciated just dorsal and inferior to the medial malleolus. The dorsalis pedis pulse is best appreciated on the dorsum of the foot between the proximal section of the first and second metatarsals, usually above the navicular bone. Palpate artery. Dorsalis pedis is palpated by hand before Doppler device is used. Place small amount of ultrasound transmission gel at landmark where the artery was located. Locate artery with Doppler device. Posterior tibial artery is located and marked with gel. Identify artery with Doppler device. Upon application of Doppler probe, arterial pulsations should be audible. If they are not, reposition probe until appropriate sound is obtained.
- 5. Do not obscure artery with cuff; you will need to be able to palpate artery and/or locate it with Doppler device. As with each appropriately identified arterial site, mark site with ultrasound transmission gel after palpation. Locate artery with device. Typically, Doppler probe must be positioned at 45-60 degrees, not at 90 degrees as shown.
- 6. Finally, divide the ankle pressure by the brachial artery pressure; the result is the ABI.

Obtained from: http://emedicine.medscape.com/article/1839449-overview#aw2aab6b4

Brachial Systolic Pressure

Anterior Tibial and Posterior Tibial Systolic Pressures

